5.5.1. Investigational Medicinal Product Return or Disposal

Study drug return and disposal will be performed as outlined in Section 9.1.7.

6. STUDY PROCEDURES

The study procedures to be conducted for each subject enrolled in the study are presented in this section and in tabular form in [Appendix 2](#) and [Appendix 3](#).

The investigator must document any deviation from protocol procedures and notify the sponsor or contract research organization (CRO).

6.1. Subject Enrollment and Treatment Assignment

It is the responsibility of the Investigator to ensure that subjects are eligible for study prior to enrollment. Please refer to Section [6.3](#) for details about randomization and treatment assignments.

6.2. Pretreatment Assessments

6.2.1. Screening Visit

Subjects will be screened within 30-days before Day 1 to determine eligibility for participation in the study. The following will be performed and documented at screening:

- Obtain written informed consent
- Obtain medical history including history of HIV-1 disease-related events and prior medications within 30 days of the screening visit
- Complete physical examination (urogenital/anorectal exams will be performed at the discretion of the Investigator)
- 12-lead ECG performed supine
- Height
- Vital signs measurement (blood pressure, pulse, respiration rate, and temperature), including weight
- Obtain blood and urine samples as described in Section [6.10](#)
- Review of adverse events and concomitant medications

Subjects meeting all of the inclusion criteria and none of the exclusion criteria will return to the clinic within 30-days after screening for the Day 1 Visit.

From the time of obtaining informed consent through the first administration of investigational medicinal product, record all serious adverse events (SAEs), as well as any adverse events related to protocol-mandated procedures on the adverse events electronic case report form

(eCRF). All other untoward medical occurrences observed during the screening period, including exacerbation or changes in medical history are to be captured on the medical history eCRF (Section 7).

6.3. Randomization

Once eligibility has been confirmed and prior to or during the Day 1 visit, the Investigator or designee will randomize the subject using the Interactive Web Response System (IWRS). Once a subject number has been assigned to a subject, it will not be reassigned to any other subject. The subject number assignment and randomization may be performed up to 3 days prior to the in-clinic Day 1 visit, provided that all screening procedures have been completed and subject eligibility has been confirmed.

6.4. Day 1 Assessments

The following evaluations are to be completed at the Day 1 Visit. **The Investigator must have received the results from the screening genotype report and confirmed eligibility before proceeding with the Day 1 visit.** The subject must complete all study procedures before being administered the study drug:

- Review of AEs and changes in concomitant medications
- Complete physical examination (urogenital/anorectal exams will be performed at the discretion of the Investigator)
- Vital signs measurement (blood pressure, pulse, respiration rate, and temperature), including weight
- Obtain blood and urine samples as described in Section 6.10
- Provide subject dosing diary to all subjects for PK collection
- Dispense study drug
- Observed first dose administration of the assigned study drugs as described in Section 5.3.
- Subjects should be instructed to take study drugs without regard to food. The subject should be counseled regarding the importance of adherence and taking their study medications at approximately the same time each day as directed by the Investigator.

6.5. Treatment Assessments (Week 4 – 96)

The following evaluations are to be completed at the end of Weeks 4, 8, 12, 24, 36, 48, 60, 72, 84 and 96 unless otherwise specified.

Study visits are to be completed within ± 2 days of the protocol-specified visit date (based on the Day 1 visit) through Week 12 and completed within ± 6 days of the protocol-specified visit date through Week 96, unless otherwise specified. The visit window at Weeks 48 and 96 will be ± 6 weeks of the protocol-specified visit date, and this clinical visit window coincides with the Weeks 48 and 96 statistical analysis window for HIV-1 RNA.

Regularly scheduled evaluations will be made on all subjects whether or not they continue to receive study drug.

- Review of AEs and changes in concomitant medications
- Complete physical examination (**Weeks 24, 48, 96**) (urogenital/anorectal exams will be performed at the discretion of the Investigator) or symptom-directed physical examination as needed
- Vital signs measurement (blood pressure, pulse, respiration rate, and temperature), including weight
- Obtain blood and urine samples as described in Section 6.10
- Provide subject dosing diary to all subjects (**Weeks 4, 8, 12 and 24**)
- Dosing diaries will be collected from subjects for the trough and post-dose PK blood sample collection as noted in Section 6.10. If a dosing diary is not returned the site may ask the subject for the time of the last dose and if it was taken with or without food.
- Document study drug dispensation and accountability for all study drugs dispensed.

6.6. Treatment Assessments (Post Week 96 until the End of Blinded Treatment Visit)

6.6.1. Post Week 96 Assessments

After Week 96, all subjects will continue to take their blinded study drugs and attend visits every 12 weeks until the last subject completes the Week 96 visit of the blinded phase. Study visits are to be completed within ± 6 days of the protocol-specified visit date unless otherwise specified.

- Review of AEs and changes in concomitant medications
- Complete physical examination (**every 48 weeks**) (urogenital/anorectal exams will be performed at the discretion of the Investigator) or symptom-directed physical examination as needed
- Vital signs measurement (blood pressure, pulse, respiration rate, and temperature), including weight
- Obtain blood and urine samples as described in Section 6.10
- Document study drug dispensation and accountability for all study drugs dispensed.

6.6.2. End of Blinded Treatment Visit Assessments

Once the last subject completes their Week 96 visit and Gilead completes the Week 96 analysis, all subjects will return to the clinic (preferably within 30 days) for an End of Blinded Treatment Visit. At the End of Blinded Treatment Visit, if safety and efficacy of B/F/TAF FDC is demonstrated for the HIV-1 and HBV coinfecting subjects following review of unblinded data, subjects in a country where B/F/TAF FDC is not available will be given the option to receive B/F/TAF FDC in an open label extension phase for up to 48 weeks, or until the product becomes accessible to subjects through an access program, or until Gilead Sciences elects to discontinue the study in that country, whichever occurs first.

Subjects who receive the open-label B/F/TAF FDC will return for study visits every 12 weeks.

Subjects who complete the study through the End of Blinded Treatment Visit and do not continue on the open label B/F/TAF FDC extension will be required to return to the clinic for a 30-Day Follow-up visit. Subjects who have discontinued drug study prior to the End of Blinded Treatment Visit will not be eligible for the open-label rollover extension; these subjects will be asked to continue attending the scheduled study visits through the End of Blinded Treatment Visit and discontinue the study after the End of Blinded Treatment Visit.

Treatment assignments will be provided to the investigators within 30 days of the last subject completing the End of Blinded Treatment Visit.

The following will be performed at the End of Blinded Treatment Visit:

- Review of AEs and changes in concomitant medications
- Complete physical examination (urogenital/anorectal exams will be performed at the discretion of the Investigator)
- Vital signs measurement (blood pressure, pulse, respiration rate, and temperature), including weight
- Obtain blood and urine samples as described in Section 6.10
- Document study drug dispensation, if applicable, and accountability for all study drugs dispensed
- Subjects who wish to continue in the Open-Label Rollover extension study will receive open label B/F/TAF.

6.7. Open-Label Rollover Extension Assessments

For purposes of study visit identification during the open-label rollover extension, study visits will be identified by the number of weeks that have elapsed between the End of Blinded Treatment Visit and the corresponding open-label study visit, and labeled with “OL” (Week 12 OL, Week 24 OL, Week 36 OL, etc.).

All subjects participating in the open label extension phase, without regard to their blinded treatment regimen, will return for study visits at Week 12 OL and every 12 weeks thereafter.

Study visits are to be completed within ± 2 days of the protocol-specified visit date based on the End of Blinded Treatment Visit through Week 12 OL and completed ± 6 days of the protocol-specified visit date every 12 weeks thereafter, unless otherwise specified.

The following will be performed at the Open-Label Extension Visits:

- Review of AEs and changes in concomitant medications
- Complete physical examination (**every 48 weeks**) (urogenital/anorectal exams will be performed at the discretion of the Investigator) or symptom-directed physical examination as needed
- Vital signs measurement (blood pressure, pulse, respiration rate, and temperature), including weight
- Obtain blood and urine samples as described in Section 6.10
- Document study drug dispensation and accountability for all study drugs dispensed.

6.8. Post-Treatment Assessments

6.8.1. Early Study Drugs Discontinuation Assessments

If the subject discontinues study drug prior to the End of Blinded Treatment Visit, the subject will be asked to return to the clinic within 72 hours of stopping study drugs for the Early Study Drugs Discontinuation Visit. The subject will be asked if they wish to continue attending the scheduled study visits through the End of Blinded Treatment Visit.

If the subject discontinues study drug during the Open Label rollover extension, the subject will be asked to return to the clinic within 72 hours of stopping the study drug for the Early Study Drugs Discontinuation Visit.

At the Early Study Drugs Discontinuation Visit, any evaluations showing abnormal results indicating that there is a possible or probable causal relationship with the study drug, will be repeated weekly (or as often as deemed prudent by the Investigator) until the abnormality is resolved, returns to Baseline, or is otherwise explained.

The following evaluations are to be completed at the Early Study Drugs Discontinuation Visit:

- Review of AEs and changes in concomitant medications
- Complete physical examination (urogenital/anorectal exams will be performed at the discretion of the Investigator)

- Vital signs measurement (blood pressure, pulse, respiration rate, and temperature), including weight
- Obtain blood and urine samples as described in Section 6.10
- Drug accountability

6.8.2. 30 Day Follow-Up Visit

Subjects who prematurely discontinue study drug during the blinded phase and refuse to continue in the study through the End of Blinded Treatment Visit will be asked to return to the clinic 30 days after the completion of the Early Study Drugs Discontinuation Visit for the 30 Day Follow-Up Visit.

Those subjects who prematurely discontinue study drug during the blinded phase and continue in the study through at least one subsequent visit after the Early Study Drug Discontinuation Visit will not be required to complete the 30 Day Follow-Up Visit.

Subjects who complete the study through the End of Blinded Treatment Visit, and refuse to participate in the open-label rollover extension will be required to return to the clinic 30 days after the completion of study drug for the 30 Day Follow-Up Visit.

Subjects who prematurely discontinue study drug during the Open Label rollover extension will be asked to return to the clinic 30 days after the completion of the Early Study Drugs Discontinuation Visit for the 30 Day Follow-Up Visit. The subject will not continue attending the scheduled study visits.

Subjects who complete the Open Label rollover extension will be asked to return to the clinic 30 days after the completion of the study drugs for the 30 Day Follow-Up Visit.

For the purpose of scheduling a 30-Day Follow-Up Visit, a ± 6 days window may be used.

The following evaluations are to be completed at the 30 Day Follow-Up Visit:

- Review of AEs and changes in concomitant medications
- Symptom-directed physical examination
- Vital signs measurement (blood pressure, pulse, respiration rate, and temperature), including weight
- Obtain blood and urine samples as described in Section 6.10

At the 30 Day Follow-Up Visit, any evaluations showing abnormal results believed to be a reasonable possibility of a causal relationship with the study drugs will be repeated weekly (or as often as deemed prudent by the Investigator) until the abnormality is resolved, returns to baseline, or is otherwise explained.

6.9. Criteria for Discontinuation of Study Treatment

Study medication will be discontinued in the following instances:

- Unacceptable toxicity, or toxicity that, in the judgment of the investigator, compromises the ability to continue study-specific procedures or is considered to not be in the subject's best interest
- Subject request to discontinue for any reason
- Pregnancy during the study; refer to [Appendix 6](#)

Note: Female subjects who become pregnant during the study will be discontinued from the study and their study treatment assignment will be unblinded by the investigator and shared with the subject.

- Development of active tuberculosis infection

Study medication may be discontinued in the following instances:

- Intercurrent illness that would, in the judgment of the investigator, affect assessments of clinical status to a significant degree. Following resolution of intercurrent illness, the subject may resume study dosing at the discretion of the investigator
- Lack of efficacy
- Subject noncompliance
- Discontinuation of the study at the request of Gilead, a regulatory agency or an institutional review board or independent ethics committee (IRB/IEC)

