5.1.1. Procedures for Breaking Treatment Codes

In the event of a medical emergency where breaking the blind is required to provide medical care to the subject, or in the case of pregnancy that occurs while on study drug, the investigator may obtain treatment assignment directly from the IXRS system for that subject. Gilead recommends but does not require that the investigator contact the Gilead medical monitor before breaking the blind. Treatment assignment should remain blinded unless that knowledge is necessary to determine subject emergency medical care or in the event of a pregnancy that occurs while on

study drug. The rationale for unblinding must be clearly explained in source documentation and on the electronic case report form (eCRF), along with the date on which the treatment assignment was obtained. The investigator is requested to contact the Gilead medical monitor promptly in case of any treatment unblinding.

Blinding of study treatment is critical to the integrity of this clinical trial and therefore, if a subject's treatment assignment is disclosed to the investigator, the subject will have study treatment discontinued. All subjects will be followed until study completion unless consent to do so is specifically withdrawn by the subject.

Gilead Pharmacovigilance and Epidemiology (PVE) may independently unblind cases for expedited reporting of suspected unexpected serious adverse reactions (SUSARs).

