6.11. Assessments for Premature Discontinuation from Study

If a subject discontinues study drug in the blinded phase of the study (for example, as a result of an AE), every attempt should be made to keep the subject in the study, and continue to perform the required study procedures until the End of Blinded Treatment Visit. If this is not possible or acceptable to the subject or investigator, the subject may be withdrawn from the study.

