- a. Evaluations to be completed within 30 days prior to Day 1.
- b. Administration of the first dose of study drug is to take place in-clinic following completion of study procedures at the Day 1 visit.
- c. Early Study Drugs Discontinuation visit to occur within 72 hours of last dose of study drug. Subjects will be asked to continue attending the scheduled study visits through the End of Blinded Treatment Visit even if the subject discontinues study drug during the blinded phase.
- d. Symptom-directed physical examination as needed. After Week 96 visit, complete physical exam to be completed every 48 weeks.
- e. HIV-1 genotype and phenotype of protease, reverse transcriptase, and integrase testing will be completed for subjects with virologic failure. Following virologic rebound, subjects will be asked to return to the clinic (2-3 weeks later) prior to the next scheduled visit or at the next scheduled study visit, for a HIV-1 RNA and HIV-1 genotype and phenotype blood draw. Based on the results of this testing, subjects should be managed according to the Virologic Rebound Schema (Section 6.14). Subjects with HIV-1 RNA ≥ 50 copies/mL at Week 48 and 96 will be asked to return for an unscheduled visit within the visit window for a retest. Subjects with HIV-1 RNA ≥ 200 copies/mL at study drug discontinuation, last visit, Week 48 or 96 will also have resistance testing conducted.
- f. Any adverse event or test showing abnormal results that is believed to have a possible or probable causal relationship with the study drug will be repeated weekly (or as often as deemed prudent by the Investigator) until the abnormality is resolved, returns to baseline, or is otherwise explained.
- g. Females of childbearing potential only. Serum pregnancy testing will be performed at the Screening visit. Urine pregnancy testing will be performed at Day 1 and all subsequent study visits (except the 30 Day-Follow-up Visit). Positive urine pregnancy tests will be confirmed with a serum test.

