Female subjects must also refrain from egg donation and in vitro fertilization during treatment and until at least 30 days after the end of relevant systemic exposure.

3) Contraception Requirements for Male Subjects

During the study, male subjects with female partners of childbearing potential should use condoms when engaging in intercourse of reproductive potential.

4) Unacceptable Birth Control Methods

Birth control methods that are unacceptable include periodic abstinence (eg, calendar, ovulation, symptothermal, post-ovulation methods), withdrawal (coitus interruptus), spermicides only, and lactational amenorrhea method (LAM). Female condom and male condom should not be used together.

5) Procedures to be Followed in the Event of Pregnancy

Subjects will be instructed to notify the investigator if they become pregnant, or are concerned they may be pregnant at any time during the study, or if they become pregnant within 30 days of last study drug dose. Subjects who become pregnant or who suspect that they are pregnant during the study must report the information to the investigator and discontinue study drug immediately. Subjects who become pregnant will be discontinued from the study and their study treatment assignment will be unblinded by the Investigator and provided to the subject.

Subjects who become pregnant while on study should receive appropriate monitoring and care until the conclusion of the pregnancy. Subjects who become pregnant while on study who are not engaged in pre-natal care that includes a routine second trimester ultrasound will be referred for ultrasonography as part of study follow-up. Instructions for reporting pregnancy and pregnancy outcome are outlined in Section [7.6.2.1](#).

**Appendix 7. Definitions of Stage 3 Opportunistic Illnesses in HIV
(CDC Guidelines)**

- 1) Candidiasis of bronchi, trachea, or lungs
- 2) Candidiasis of esophagus
- 3) Cervical cancer, invasive
- 4) Coccidioidomycosis, disseminated or extrapulmonary
- 5) Cryptococcosis, extrapulmonary
- 6) Cryptosporidiosis, chronic intestinal (> 1 month duration)
- 7) Cytomegalovirus disease (other than liver, spleen or nodes)
- 8) Cytomegalovirus retinitis (with loss of vision)
- 9) Encephalopathy, HIV-related
- 10) Herpes simplex: chronic ulcer(s) (> 1 month duration); or bronchitis, pneumonitis or esophagitis
- 11) Histoplasmosis, disseminated or extrapulmonary
- 12) Isosporiasis, chronic intestinal (> 1 month duration)
- 13) Kaposi's sarcoma

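### Blinded phase: the protocol both removes a participant who becomes pregnant from the study and keeps her in follow-up; on the removal reading, scheduled ALT and HBV DNA end 24–39 days after HBV-active drug stops

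*Protocol*

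**What the plan says.** Two provisions take her out of the study. Protocol 6.9, in a note under the rules for stopping study medication: "Female subjects who become pregnant during the study will be discontinued from the study". Appendix 6, item 5: "Subjects who become pregnant will be discontinued from the study and their study treatment assignment will be unblinded by the Investigator".

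Four provisions keep her in.

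- Section 5.1.1 lists pregnancy on study drug as a ground for unblinding, says that an unblinded subject stops study treatment, and adds: "All subjects will be followed until study completion unless consent to do so is specifically withdrawn by the subject".
- Section 6.5: "Regularly scheduled evaluations will be made on all subjects whether or not they continue to receive study drug".
- Section 6.11, for anyone stopping drug in the blinded phase: "every attempt should be made to keep the subject in the study, and continue to perform the required study procedures". It allows withdrawal where this is not possible or not acceptable to the subject or investigator.
- Appendix 2 footnote c asks subjects to "continue attending the scheduled study visits through the End of Blinded Treatment Visit even if the subject discontinues study drug during the blinded phase".

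None of the four excepts pregnancy. Section 7.6.2.1 does not settle the matter: it cites 5.1.1 for unblinding and also refers to Appendix 6. Section 6.10.2 says that a woman with a positive serum test is discontinued, without saying whether from drug or from study.

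The point concerns the blinded phase only. In the open-label extension, 6.8.2 ends scheduled visits for everyone who stops drug.

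**The concern.** Both regimens contain a drug that 1.6 describes as approved for hepatitis B (TAF in one arm, TDF in the other), and pregnancy stops that drug at once. The protocol recognises hepatitis B exacerbation after stopping: 7.5.4.2 is written for it. That section, however, acts on a laboratory result already in hand and schedules no test that would find one. The weekly repeats in 6.8.1 and 6.8.2 likewise apply only to results already abnormal at those visits. The pregnancy care required by 7.6.2.1 and Appendix 6, and the handover to the treating physician in 6.13, name no ALT or HBV DNA test.

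Which instruction a site follows therefore decides whether this participant is offered the scheduled liver monitoring that other early stoppers in the blinded phase are offered. What is at stake is her safety monitoring and consistent conduct across sites. The risk falls mainly on a woman who does not start other HBV-active therapy; 7.5.4.2 itself covers only subjects on no post-study HBV therapy.

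**Working it through.** The plan prints no figure for this interval, so there is nothing to reproduce. The check is visit-window arithmetic.

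**1. Last scheduled sample if she leaves the study (6.9).** Inputs: discontinuation visit within 72 hours of stopping, that is 0–3 days (6.8.1); 30-Day visit counted from that visit, window ± 6 days (6.8.2). Appendix 2 marks chemistry, which includes ALT, and HBV DNA at both visits.

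- Earliest: 0 + 30 − 6 = 24 days after the last dose.
- Latest: 3 + 30 + 6 = 39 days after the last dose.
- Scheduled after that: none.

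This is the generous reading. Section 6.8.2 words the 30-Day visit for subjects who refuse to continue. Appendix 2 footnote p, which covers early stoppers who do not continue in the study, is what brings in a woman removed by protocol. Without it, scheduled testing would end at the discontinuation visit, 0–3 days after stopping.

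**2. Scheduled visits if she is retained (5.1.1, 6.5, 6.11) and attends.** Visits fall at Weeks 4, 8, 12 and every 12 weeks to Week 96 (6.5), with HBV DNA at each (6.10.1). The stop dates are illustrations.

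| Drug stopped at | Visits left through Week 96 | Count | In first 24 weeks off drug (nominal) |
|---|---|---|---|
| Week 12 | 24, 36, 48, 60, 72, 84, 96 | 7 | Weeks 24, 36: 2 |
| Week 24 | 36, 48, 60, 72, 84, 96 | 6 | Weeks 36, 48: 2 |
| Week 48 | 60, 72, 84, 96 | 4 | Weeks 60, 72: 2 |
| Week 4 | 8, 12, 24, 36, 48, 60, 72, 84, 96 | 9 | Weeks 8, 12, 24 (4, 8, 20 weeks off): 3 |
| Just before Week 4 | 4, then as for Week 4 | 10 | Weeks 4, 8, 12, 24: 4 |

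The counts are upper bounds because attendance is her choice. Section 6.8.1: "The subject will be asked if they wish to continue attending the scheduled study visits through the End of Blinded Treatment Visit".

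**3. Effect of the waiver.** Subjects who stay for at least one later visit "will not be required to complete the 30 Day Follow-Up Visit" (6.8.2; footnote p agrees). Her first sample after the discontinuation visit is then the next regular visit:

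- Stop on the nominal Week 12, 24 or 48 date: next visit 12 × 7 = 84 days later, ± 6 days, giving 78–90 days.
- Stop on the nominal Week 36 or 84 date: the next visit is Week 48 or 96, whose window is ± 6 weeks (6.5), so 84 ± 42 gives 42–126 days.
- Stop on the nominal Week 4 date: 28 ± 2 gives 26–30 days. A mid-interval stop also brings the next visit sooner.

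For most stops on a visit date after Week 12, retention alone would therefore push her next sample beyond the present 24–39 days, while adding samples later.

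**The case against.** The strongest reply is that the specific rule governs. The note in 6.9 and Appendix 6 are written for pregnancy, they agree, and 7.6.2.1 cites 5.1.1 for unblinding only; a site would probably follow them. This does not remove the conflict. Section 5.1.1 also deals with pregnancy by name and still says that all subjects are followed.

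Second, testing that ends at about 30 days is the protocol's general rule for subjects who refuse to continue, for open-label stoppers and for completers who do not roll over. That stands. The difference is that in the blinded phase those who stop drug early are asked to stay, whereas 6.9 removes her. It also stands that keeping the 30-Day visit for her alone would treat her differently from others under the same waiver, so that edit is secondary.

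Third, the harm is not shown. The documents give no timing for flares, 1.6 says HBV treatment is important in all co-infected patients, and she is told her assignment, which may help her move to other therapy. This stands as a limit on weight. A reader might infer that flares would be missed; the documents do not support that.

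Fourth, she is not abandoned. Appendix 6 requires care to the end of the pregnancy, with ultrasound referral for some women as part of study follow-up, and 7.5.4.2 can run up to 6 months from onset of an exacerbation. Reading 6.9 as ending all follow-up would go too far. What ends is scheduled ALT and HBV DNA.

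**Conclusion.** The contradiction is real, and no reading of the text removes it. On the 6.9 reading, the last scheduled ALT and HBV DNA fall 24–39 days after HBV-active drug stops, assuming footnote p gives her the 30-Day visit. On the 5.1.1 reading, up to 7, 6 or 4 visits through Week 96 remain after a stop at Week 12, 24 or 48, if she attends. Nominally 2 of these fall in the first 24 weeks off drug. Two is not a ceiling for every stop date: a stop at or before Week 4 gives 3–4.

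This should be corrected as a matter of participant safety and consistent conduct. A reader might infer damage to the efficacy comparison, but none is claimed: the expected number of pregnancies is not stated and, with mandatory contraception, is presumably very small. The clinical harm is plausible but unquantified.

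**What to change.** Core edit: in 6.9, 6.10.2 and Appendix 6, say that she is discontinued from study drug and is offered the scheduled blinded-phase visits, including ALT and HBV DNA, unless she withdraws consent. This matches 5.1.1, 6.5 and 6.11.

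Secondary edit: in 6.8.2 and Appendix 2 footnote p, keep her 30-Day visit even if she continues, so that retention does not delay her next sample.

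Excepting pregnancy in 5.1.1 instead would remove that section's conflict with 6.9 but leave the sampling gap. The rules on stopping drug, unblinding and the open-label extension do not change.

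The cost is wording in five places, plus some existing visits and blood draws (including fasting and storage samples) for very few participants, who may decline.
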